Step ladder insertion technique: The AVF site will be cleaned with 2% chlorhexidine/alcohol 70% prior to needle insertion. If the patient develops contact dermatitis, the AVF site will be cleansed with 2% cholorhexidine, 70% alcohol, povidone iodine or antibacterial soap alone. Sites will be rotated with needles placed at least 2-3cms between needle tips.

Buttonhole insertion technique: The AVF site will be cleaned as above except cleansing will occur before and after buttonhole scab removal. A minimum of 2 buttonholes will be developed for patients undergoing double needle hemodialysis (1 for single needle) by a nurse or patient (at the discretion of the health care team) trained in the technique.

Buttonhole sites will be created at a 20-30 degree angle at least 3 cm from the arterial or venous anastomosis. Once the buttonhole is established with sharp needles, blunt needles will be used. At this time, the patient will be instructed on needle insertion technique if they were not taught to develop the buttonholes initially. Scabs will be removed from the buttonholes either with an alcohol or saline soaked gauze; the use of needles or tweezers to remove scabs will be discouraged.. Post hemodialysis, mupirocin (or other suitable antimicrobial cream if patient develops contact dermatitis/allergy, for example: polysporin, betadine ointment or PHMB antimicrobial dressings) will be applied to the buttonhole sites to reduce the risk of infection.

Time to Train

Patients will be trained according to usual home dialysis unit policies with the exception of the needle insertion protocol. Any difficulties with training needle insertion will be documented by the nurse educator. The time required to teach proficiency in self cannulation will be documented (the number of days required for the patient to competently place their own needles without the assistance of the dialysis nurse). Total training time will be the numbers of days required from start of training to discharge to home. Any missed days secondary to statutory holidays, appointments or other illness unrelated to access needle insertion technique will not be included in the training days calculation. If a patient has to return to the home dialysis unit to develop a new buttonhole site, the training time will also be documented and added to the total training time.

AVF Access Complications

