have a similar impact on training time, 69 patients per groups would give us 80% power to detect this difference. The number required in the trial increases to 107 if the difference is 4 days.

Analysis

For the purposes of the pilot study, basic demographic characteristics of the included and excluded patients will be described using appropriate descriptive statistics. This data will be retrospectively collected on patients who were not enrolled in the study. The percent of qualified patients enrolled in the study for the pilot study to be successful will be $\geq 70\%$. The secondary outcomes will be analyzed on an intent to treat basis upon completion of the main study assuming that this trial is feasible. The comparison of mean training times will be done with an un-paired t-test. A linear regression analysis will also be undertaken to examine predictors of training time including age, sex and Charlson comorbidity score in addition to needle insertion technique. Any differences in pain scores depending of frequency of cannulation will be explored within cannulation techniques. If no differences exist by frequency of cannulation, the data will be combined and the median pain scores will be assessed with a Wilcoxon rank sum test. The different types of complications and costs will be categorized and the overall mean differences will be assessed with an unpaired t-test. Any differences in outcomes by frequency of cannulation will also be explored within each of the secondary outcomes.

For patients who return to train on cannulation technique (started home HD with a CVC or other access that failed); their data will not be included in overall training time but all other study outcomes will be tracked and included in the analysis infections and complications.

The retrospectively collected demographic data will be analyzed in order to describe the patient population.

Data Safety Monitoring Board

Drs. [name] and [name] in addition to [name] (vascular access coordinator) have agreed to monitor the outcomes of this study. If we detect infection rates that are comparable to or greater to the benchmark for central venous catheters as adopted by the Ottawa Hospital - the study will be stopped (external benchmark bacteremia rate of 4.6 per 100 patient months, Nephrology News and Issues 2005, 37-43)

Study Investigators

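### Training time has a value only for patients discharged home, and no rule covers randomized patients who never get there, so by default the t-test compares completers

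*Combined protocol and SAP*

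**What the plan says.** The section *Time to Train* defines two measures. Proficiency time is "the number of days required for the patient to competently place their own needles without the assistance of the dialysis nurse". For the overall measure, "Total training time will be the numbers of days required from start of training to discharge to home". Two rules then adjust the count: days missed for reasons unrelated to needling are taken out, and days spent returning to develop a new buttonhole are added.

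The section *Analysis* states: "The secondary outcomes will be analyzed on an intent to treat basis upon completion of the main study assuming that this trial is feasible". For this outcome, "The comparison of mean training times will be done with an un-paired t-test", with a linear regression on age, sex, Charlson score and technique alongside. One group is explicitly left out of training time, namely patients returning to train on cannulation after another access failed: "their data will not be included in overall training time but all other study outcomes will be tracked".

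The *Sample Size Calculation* sizes the definitive trial on this outcome (mean 27.7 days, SD 10.4, difference 5 days, 69 per group, 80% power). The section *Study Investigators* says pilot data will be kept for the definitive trial if feasibility is established, the sample size is achievable and the protocol needs no change.

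**The concern.** Both measures end at a success: competent self-needling, or discharge home. A randomized patient who abandons training, changes modality or otherwise never goes home reaches neither. The t-test needs one number per patient, and the plan gives no imputation, censoring, ranking or sensitivity rule for patients without one. Followed as written, the analysis drops them after randomization, which does not fit the intent-to-treat label.

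Failure to learn self-cannulation is arguably the worst result on this outcome. It could also depend on technique, because the background section argues that a formed tract may make needling simpler. If so, a technique that prevents failures gets no credit for it. If those failures would also have been the slow trainees, losing them shortens the mean of the arm that failed more often. The error could run either way: a real buttonhole benefit could be understated, or an apparent one created. What is at stake is the outcome on which the definitive trial is sized.

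**Working it through.** **Inputs.** From *Sample Size Calculation*: mean 27.7 days, SD σ = 10.4, difference δ = 5 days (alternative 4), 69 per group (107 for 4 days), power 80%. Alpha is not stated; two-sided 0.05 is assumed. No training-failure rate is given, so the rates below are assumptions.

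**Step 1: the plan's own figures.** n per group = 2(1.960 + 0.842)²σ²/δ².
- δ = 5: 2 × 7.849 × 108.16 / 25 = 67.9, so 68. The t-distribution version gives 68.9, so 69.
- δ = 4: 2 × 7.849 × 108.16 / 16 = 106.1, so 107. The t-distribution version gives 107.1.

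Both figures reproduce on complete data. One-sided 0.05 would give 54 and 84, which do not match. Neither figure contains an allowance for patients without a training time.

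**Step 2: spurious shift if the slowest fraction f of an arm is lost.** For a normal outcome, the mean of those who remain falls by σφ(c)/(1 − f), where c = Φ⁻¹(1 − f).
- f = 5%: 10.4 × 0.1031 / 0.95 = 1.13 days
- f = 10%: 10.4 × 0.1755 / 0.90 = 2.03 days
- f = 20%: 10.4 × 0.2800 / 0.80 = 3.64 days

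The spurious difference between arms is the difference between two such shifts. The last column is the simulated rejection rate of the nominal 5% t-test, with 69 randomized per arm and no true difference.

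| Failing, arm A vs arm B | Spurious shift (days) | False rejection |
|---|---|---|
| 5% vs 0% | 1.13 | about 10% |
| 10% vs 0% | 2.03 | about 21% to 23% |
| 10% vs 5% | 2.03 − 1.13 = 0.90 | about 8% |
| 20% vs 10% | 3.64 − 2.03 = 1.61 | about 18% |
| 10% vs 10%, same mechanism | 0 | 5% |

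The table removes patients beyond a fixed population cut-off. The range for 10% vs 0% reflects method: that cut-off gives about 21%, and deleting exactly the slowest seven of 69 gives about 23%.

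**Step 3: effect on a true 5-day benefit.** With the failures in the step-ladder arm only, 5% vs 0% makes the benefit appear as 5 − 1.13 = 3.9 days, with power about 62%. For 10% vs 0% it appears as 5 − 2.03 = 3.0 days, with power about 41%. With the failures in the buttonhole arm, the same shifts would be added to the benefit.

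**Step 4: failure unrelated to speed.** With 10% vs 0% lost at random, the simulated shift is zero, rejection stays at about 5%, and power for 5 days is about 78%. If 10% of both arms are lost at random, 62.1 per arm remain and power is Φ(5/(10.4√(2/62.1)) − 1.96) = Φ(0.72) = 76%. The cost is then precision, without bias.

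**The case against.** The strongest reply is that the plan never says training failures are excluded. It promises intent to treat and names only one exclusion, the returning patients. That is correct as to wording, and a reader should not infer a stated completers-only rule. What stands is narrower: the definition gives these patients no number, and nothing else in the plan does, so the default is omission.

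A reader might also infer that the direction of bias is certain whatever the failure rate. It is not. It depends on which arm fails more and on whether those who fail are slow learners; loss through death, transplant or a move need not be related to speed. If only three of seven failures in a 10% vs 0% split are the slowest trainees, the shift is about 0.9 days and rejection about 9%. The table in the working is therefore an upper illustration.

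The *Exclusion Criteria* remove foreseeable loss from the program, and life expectancy must exceed 12 months. This lowers non-completion but does not address failed training. The exclusion of returning patients is a baseline category and does not cover it either.

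Finally, ranking every non-graduate worst would penalise an arm for events unrelated to needling. That sits badly with the plan's own rule for missed days: "Any missed days secondary to statutory holidays, appointments or other illness unrelated to access needle insertion technique will not be included in the training days" count. This objection is sound, and the fix is narrowed to respect it.

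**Conclusion.** The gap is real: an outcome that exists only at discharge home, a t-test on means and an intent-to-treat label do not fit together without a rule for patients who never go home. Bias requires two conditions that the documents neither establish nor rule out: failure that differs by technique, and failure concentrated among slower trainees. If both hold, the spurious shift is roughly 1 to 2 days over the rates illustrated, against a design difference of 5 days. If failure is unrelated to speed, or equal in both arms by the same mechanism, the shift is zero.

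A reader might conclude that the pilot's result is compromised. The documents do not support that: its primary outcome is feasibility, with success set at 70% or more of qualified patients enrolled, and training time plays no part in it. The point matters for the definitive trial and for what the pilot must record now.

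**What to change.** Keep the t-test in patients who go home. For all randomized first-time trainees, add:

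1. By arm, the proportion discharged home on self-cannulation, with the reasons for non-completion.
2. A supportive Wilcoxon rank sum analysis of training days (the plan already uses this test for pain), with patients who stop training for needling-related reasons ranked worst. Add a sensitivity analysis that ranks all non-graduates worst.

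Record training outcome and reason for non-completion on the case report form from the pilot onward, because pilot data may be retained. The *Study Overview* describes a log of trainees, candidates, randomized patients and reasons for not participating, and *Time to Train* has needling difficulties documented. Neither describes a field for training outcome, so it should not be assumed to be captured already.

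The cost is one or two form fields and a few lines of analysis text. The downside is that the rank analysis gives no difference in mean days, so the t-test remains the source of that estimate. Label: cheap improvement.

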The insertion of needles into an AVF has traditionally been via the step ladder or continuous site rotation technique. However, the buttonhole method was introduced in the 1970's in an attempt to address some of the challenging issues associated with AVF accesses.¹⁹ In the buttonhole technique, a constant site is used for needle placement that ultimately results in a fibrous tract. Once the tract has formed blunt needles can be used instead of sharp needles for each treatment. The presence of a tract may simplify the needle insertion technique and lead to enhanced patient confidence with needle placement. Although no studies have reported training times in association with needle insertion technique, Pipkin et al have demonstrated a mean reduction in training time for home hemodialysis patients of 5 days when a central venous catheter was used for an access compared to an AVF.²⁰ It is reasonable to assume that well established buttonholes may also lead to a similar reduction in training times. Other reported benefits of buttonhole cannulation include less painful needling,²¹⁻²⁴ fewer needle infiltrations,^{19,24,25} fewer interventions²⁶ and a reduction in aneurysm size.²³ While earlier studies demonstrated a reduction in pain with buttonhole needling, more recent studies show either no reduction in pain,^{27,28} or even an increase in pain.²⁶ However, the effect of frequency of use on the maintenance of the buttonhole and the perception of pain has not been explored. Importantly however, there has also been increasing concern about the potential for an increased risk of infection using the buttonhole cannulation technique with estimates of *Staphylococcus aureus* (*S. aureus*) bacteremia for patients receiving high dose dialysis between 0.15 to 0.60 episodes per 1000 patient-days across 4 studies.²⁹⁻³² In an indirect comparison between high dose home hemodialysis with buttonhole cannulation versus in-centre conventional hemodialysis with rope-ladder cannulation, the relative risk for bacteremia ranged between 30 to 120. Importantly, *S. aureus* bacteremia was associated with devastating consequences, including septic arthritis, septic pulmonary emboli, vertebral osteomyelitis, and death in a single centre's experience.³³ In one small study, the risk of infection associated with buttonhole

cannulation was prevented by the application of topical mupirocin at the buttonhole sites post hemodialysis.

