Differences between Conventional In-Centre and Home Hemodialysis

Although ease of cannulation is important in-centre, it is even more important for patients at home. It is unclear if the potential ease of use of buttonhole cannulation might lead to enhanced home hemodialysis recruitment rates and reduced training time. The ease of use of CVCs likely contributed to the decreased training time that was required for patients with this type of access in the Frequent Hemodialysis Network Trial. There is emerging controversy about reduced pain on needle insertion with buttonhole cannulation in centre. However, it is unclear if using the buttonholes more frequently might result in reduced cannulation pain secondary to 'enhanced' maintenance of the fibrous tract. Lastly, for patients who are treated in-centre, needles are typically inserted by skilled allied health team members. At home, needles are inserted by the patient or a family member helper who must be trained to perform home hemodialysis. It is unclear if allied health team members are more likely to follow strict rules for cleanliness compared to patients at home such that infection risks might be less in-centre. Also, the enhanced frequency of use of the buttonholes for high dose hemodialysis might be associated with an increased risk of infection.

Summary and Conclusions

There is increasing interest in high dose home hemodialysis therapies. Although both needle cannulation techniques have been used for home hemodialysis, the relative benefits and risks of the two techniques have never been explored in a randomized controlled trial. The potential advantages of buttonhole cannulation for this patient population may be enhanced recruitment, reduced training time, reduced aneurysm formation and a reduced number of interventions. The reduction in training time may result in significant savings to the hospitals in which reimbursed training days are fixed. The benefits may be offset by the potential for an increased risk of infection. However, the potential benefits and risks of buttonhole cannulation versus step-ladder cannulation remain speculative as they have not been studied in a rigorous prospective trial of home hemodialysis patients treated with high dose hemodialysis.

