Study Design: The proposed 12 month vanguard study will be a randomized controlled trial of patients training for home hemodialysis. The primary outcome for the proposed study is feasibility to recruit to the two different needle cannulation arms and coordination of the study centres. Additionally, demographic data will be retrospectively collected on patients who trained to do home hemodialysis, but were not eligible for the study to help explain recruitment challenges.

Patient Population:

Inclusion Criteria

The following inclusion criteria will be used: 1. Adult patients > 18 years old, 2. Training for home hemodialysis using self cannulation, 3. Returning to train to use an AVF (i.e. went home using a CVC or another access that has failed), 4. Able to give informed

consent, 5. Arteriovenous fistula (patients with segments of grafts that are not at the sites of needle insertion may be included), and 6. Life expectancy of greater than 12 months

Exclusion Criteria

The following exclusion criteria will be used: 1. Potential to be lost from the program within 12 months of training (planned living donor transplant, transfer to PD or move from training centre catchment area), 2. Short segments or aneurysms within the AVF that the attending nephrologist believes require buttonhole cannulation, 3. Mechanical heart valves, 4. Patients who require intradermal lidocaine for needle insertion

Study Overview

After obtaining informed consent, basic demographic data will be collected including age, sex, cause of end stage renal disease, arteriovenous access history [date of creation, previous interventions (angioplasties, surgical revisions), previous infections] and comorbidity information to calculate the Charlson comorbidity index. Demographic data will also be retrospectively collected on patients who were training for home hemodialysis but were not eligible to participate in the study.

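### Total training time ends at discharge home whatever the access or cannulator, and later days are added only for a new buttonhole site, so patients who do not master AVF self-cannulation are scored as completed trainees

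*Combined protocol and SAP*

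**What the plan says.** The Time to Train section defines the outcome: "Total training time will be the numbers of days required from start of training to discharge to home". Missed days unrelated to needling are removed. One kind of later day is put back: "If a patient has to return to the home dialysis unit to develop a new buttonhole site, the training time will also be documented and" is then added to the total.

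The same section keeps a separate measure: "The time required to teach proficiency in self cannulation will be documented", counted as days until the patient places the needles without the nurse's help. The nurse educator also notes any difficulty in teaching needle insertion.

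Self-cannulation appears in the Inclusion Criteria as "Training for home hemodialysis using self cannulation". That is a condition for entry, not for stopping the clock.

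The Analysis section compares mean training times by unpaired t-test and analyses secondary outcomes by intent to treat. For patients who return to train on cannulation after starting at home on a catheter or another failed access, it says that "their data will not be included in overall training time". No rule covers a randomized patient who changes access, relies on a helper or never reaches proficiency.

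**The concern.** The outcome is meant to show whether one cannulation technique is learned sooner than the other. As defined, the clock stops at an administrative event that can occur without the skill having been learned. Two routes are recognisable from the documents. The third inclusion criterion describes people who went home on a different access: "Returning to train to use an AVF (i.e. went home using a CVC or another access that has failed". The background on home treatment says that "needles are inserted by the patient or a family member helper".

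The rule for later days is also uneven. Developing a new buttonhole site is specific to buttonhole cannulation. A step-ladder patient who comes back because of needling difficulty adds nothing to total training time, and neither does a buttonhole patient who is re-trained without a new site.

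Training time is the first secondary objective and the basis of the definitive trial's sample size, and training days enter the cost comparison. The Study Investigators section allows pilot data to be retained for the definitive trial. If access and cannulator at discharge are not recorded now, those patients may not be classifiable later.

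**Working it through.** **Inputs from the documents** (Sample Size Calculation): mean 27.7 days and SD 10.4 for fistula trainees; assumed difference 5 days; 69 per group for 80% power; 107 if the difference is 4 days. The 5 days come from a catheter-versus-fistula comparison, described in the background as a "mean reduction in training time for home hemodialysis patients of 5 days when a central venous catheter was used for an access".

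**Assumptions:** two-sided 5% level and 1:1 allocation, neither of which is stated. One-sided 5% would give 54 and 84 per group (normal approximation), which does not match the plan.

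**Step 1: the plan's own figure.** For a two-sample t-test with standardized difference 5/10.4 = 0.481, the required number is 68.9, so 69 per group. For 4/10.4 = 0.385 it is 107.1, against the plan's 107. Power at 69 per group for 5 days is 80.1%. The sample-size arithmetic is sound.

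**Step 2: effect of the scoring rule.** Let f be the excess proportion in one arm discharged without fistula self-cannulation, and g the average number of days by which each is under-scored. The mean of that arm is too short by f × g. If the excess is in the step-ladder arm, the recorded difference is

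recorded difference = 5 − f × g.

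The documents give neither f nor g. For illustration, g = 5 days, the documents' catheter-versus-fistula gap, with SD held at 10.4 and 69 per group:

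| Excess f in step-ladder arm | Recorded difference (days) | t-test power | n per group for 80% |
|---|---|---|---|
| 0 | 5.00 | 80.1% | 69 |
| 5 points | 5 − 0.05 × 5 = 4.75 | 75.9% | 77 |
| 10 points | 5 − 0.10 × 5 = 4.50 | 71.3% | 85 |
| 20 points | 5 − 0.20 × 5 = 4.00 | 61.1% | 108 |

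The last n is 107.1 rounded up; the plan has 107.

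**Step 3: the opposite direction.** If the excess is in the buttonhole arm, the recorded difference is 5 + f × g: 5.25 to 5.5 days for 5 to 10 points. With no true difference, 5 to 10 points produce a spurious buttonhole advantage of 0.25 to 0.5 day, and the test rejects in 5.2% to 5.9% of trials instead of 5%. At 20 points these become 1 day and 8.7%.

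**Step 4: later training days.** The same formula applies to re-training that is not added: f is then the excess proportion re-trained without a new buttonhole site, and g the uncounted days each. No figure for either is given.

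**The case against.** The strongest reply has five parts.

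- **Failures can be identified.** Time to proficiency and training difficulties are already recorded, so a patient with no proficiency time stands out. This is true, but the Analysis section specifies no analysis of proficiency time and no scoring for those who never reach it.
- **Re-training is not lost to the trial.** Costs of Vascular Access counts re-training days, and the secondary objectives list re-trains for needling difficulty as a complication. This stands. The gap is in total training time only, and it means that the data to close it will largely exist.
- **The event is not shown to happen after randomization.** The inclusion criterion describes history before entry, and the helper sentence is general background. This stands as a limit on size; the definition still has no rule if the event occurs.
- **A short time does not follow.** A reader might infer that a failed cannulator is recorded as a fast trainee. The documents do not support that. Days spent attempting to needle are counted, the 5-day saving is an average for people who trained on a catheter, and no training time is given for helper needling. The recorded time is possibly too short, no more.
- **Days to discharge is a legitimate resource measure** and gives every discharged patient a value. This stands. Ending the clock only at successful self-cannulation would leave never-proficient patients without a value in the main test and create informative missingness.

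A reader might also take the exclusion in the Analysis section to drop randomized patients who go home on a catheter and later return. Its wording most naturally means patients who entered under inclusion criterion 3, so one clarifying sentence is enough.

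**Conclusion.** The definition has a gap. Total training time treats discharge without fistula self-cannulation as completed training, and it adds later days for only one reason, which belongs to buttonhole cannulation. The direction of bias depends on which arm has more such patients: an excess in step ladder hides a true saving, and an excess in buttonhole exaggerates it.

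The size is unknown. Under a 5-day shortfall per patient and a 5 to 10 point excess in step ladder, a 5-day difference is recorded as 4.75 to 4.5 days and power falls from 80% to about 76% to 71%. A much larger loss can be constructed. If the slowest 10% of a normal distribution (mean 46.0 days) were all in one arm and all went home at 22.7 days, the shift would be 0.10 × (46.0 − 22.7) = 2.3 days and power about 33%. Nothing in the documents supports that case: it requires people who would need more than 41 days to be sent home at day 22.7.

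The pilot's primary outcome, feasibility, is not affected. The point matters for the definitive comparison and for retained pilot data, and is worth correcting while the forms are being developed.

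**What to change.** **Time to Train.** Keep days from start of training to discharge as the base value in the main intent-to-treat t-test, so that every discharged patient has one. Replace the provision for a new buttonhole site by one that adds in-unit days of any later fistula cannulation training or re-training, in either arm.

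**Data forms.** Record at discharge the access in use and who places the needles. Report by arm the number discharged without fistula self-cannulation.

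**Analysis.** Prespecify a rank-based sensitivity analysis that gives the worst rank to patients who never reach self-cannulation, identified from the proficiency time already recorded. State that the exclusion from overall training time applies only to patients who entered under inclusion criterion 3.

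**Cost.** Two form fields, a few sentences and one extra analysis. Re-training days are already needed for the cost outcome, and the Study Overview has the forms pilot tested at two sites before the electronic version is built. The change concerns measurement only and alters no discharge or treatment decision.
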